The study is a population-based randomized controlled trial. To reduce potential for contamination, treatment assignment will be determined at the level of the household, such that if there are multiple eligible participants per household, they will receive the same treatment. Households will be randomized to study arm *ex ante*, i.e. before going into the field. *Ex ante* randomization has two benefits. First, as a quality control, *ex ante* randomization limits the opportunity for violations of treatment assignment. Second, because the study is nested in the AHRI population surveillance, *ex ante* randomization enables us to achieve balance across study arms with respect to several baseline characteristics of interest among eligible participants. We will use a constrained randomization approach to achieve approximate balance on: sex, age, whether the person was in school, orphans status, HIV positive status, HIV negative status (unknown is the third category), and household asset quintile. These factors were selected because of their potential influence on survival expectations. (For further details on randomization procedures, please see Appendix C.)

We note that sampling and randomization will be conducted using AHRI's public use (de-identified) data. We will provide a list of public use identifiers and treatment assignments to AHRI's data management staff, and they will create an operational database to be used during data collection. Information on the characteristics above (e.g. HIV status) will never be linked with personally-identifiable information.

Participants will be randomized using a ratio of 50% active treatment, 25% attention placebo control, 25% pure control.

	Active Treatment Video	Attention Placebo Video
Arm 1, Active Treatment	X	
Arm 2, Attention Placebo Control		X
Arm 3, Pure Control		

A8.3. Blinding

Participants and interviewers

During recruitment, consent, and the first half of the baseline survey, participants and interviewers will be blinded as to the participant's treatment assignment. Randomized treatment assignment will be revealed at the moment when participants received the intervention. However, we will not indicate to the participants whether the video they see is the treatment or attention placebo video.

Researchers

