We will additionally assess balance on all primary and secondary outcomes described above that are measured at baseline.

Through linkage to the AHRI surveillance, we will additionally assess balance on: whether the person has a child; household size; distance to the nearest clinic, whether anyone in the household died from HIV in the prior 10 years; whether anyone in the household is receiving public sector ART at time of baseline.

For each baseline covariate, we will report a t-test for the null hypothesis of equal means in Arm 1 vs. Arms 2+3 (pooled).

B4. Statistical analysis of treatment effects

All statistical analyses will involve comparisons across the treatment arms described above. For each outcome, we will generate the following data:

Example Results Table (fake data)

	Sample Means				Treatment Effect Estimate (95% CI)		
	Arm 1, n=XXX	Arms 2+3, n=XXX	Arm 2, n=xxx	Arm 3, n=xxx	Crude difference	Adjusted for design variables ^a	Adjusted for design, strong predictors, and baseline imbalance ^b
Outcome 1	1.2	1.5			-0.3 (-0.5 to 0.2)	-0.3 (-0.5 to 0.2)	-0.3 (-0.5 to 0.2)
			1.7		-0.5 (-0.8 to 0.0)*	-0.5 (-0.7 to 0.0)*	-0.5 (-0.7 to 0.0)*
				1.4	-0.3 (-0.5 to 0.3)	-0.3 (-0.5 to 0.2)	-0.3 (-0.5 to 0.2)
Outcome 2							
...							
Outcome k							

^aDesign variables are those variables on which balance was explicitly assessed during randomization. ^bStrong predictors of the outcome are those factors in the baseline balance table that are adjusted differences include regression adjustment for stratifying variables, variables used in the constrained randomization, and variables that were not balanced at baseline despite randomization (p-value <0.1 in F-test).

Sample means will be reported for Arm 1, the combined control (Arms 2+3), and for Arm 2 and 3 separately. When assessing changes from baseline to follow-up, we will simply define the outcomes as within-subject “differences” to facilitate comparisons with other outcomes observed only after the intervention.

Crude comparisons of outcomes between treated and comparison arms will be assessed in linear regression models, regressing the outcome on an indicator for treatment arm and indicators for week-block, a stratification variable. We will adjust our standard errors for clustering at the household level, given that error terms without households may be correlated.

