Adjusted effect estimates. We will estimate adjusted effect estimates in multivariate linear regression models. Adjustment for covariates in an RCT has three aims[23]:

- (design variables) to obtain appropriate standard errors when conducting stratified or constrained randomization;
- (strong predictors of the outcome) to reduce residual variance in the outcome, leading to smaller standard errors and narrower confidence intervals; and
- (factors with strong baseline imbalance) to eliminate the impact of any imbalances on observed baseline factors, despite randomization

(a) In our adjusted analyses, we will include the following design variables:

- Stratification variables: week block
- Constrained randomization variables: sex, age, whether the person was in school, orphan status, HIV positive status, HIV negative status (unknown is the third category), and household asset quintile

(b) We will include the following variables believed *a priori* to be strong predictors of HIV testing and human capital investment:

- Distance to nearest clinic
- Baseline subjective life expectancy
- Baseline beliefs about lifetime HIV infection risk

(c) Finally, to eliminate imbalances on observables, we will adjust for variables with $p < 0.1$ for the t-test of differences between Arm 1 and Arm 2+3.

B5. Subgroup analyses

The informational intervention is expected to have the greatest impact for individuals with low baseline survival beliefs and for individuals with high baseline beliefs about lifetime chances of contracting HIV.

Perceived likelihood of lifetime HIV infection. The impact of the informational video is likely to vary by baseline perceived risk of lifetime HIV infection. We will assess for linear effect modification of our primary outcomes by perceived lifetime infection risk.

Baseline survival expectations. The impact of the informational video is likely to vary by baseline survival expectations, with the greatest potential shift in beliefs for individuals with previously low survival expectations. We will assess for linear effect modification of our primary outcomes by baseline subjective life expectancy.

Finally, we will assess effect modification by age (continuous, 18-25) and sex of the respondent (M/F).

B6. Robustness checks

We will subject our primary results (Arm 1 vs. Arms 2+3 for primary outcomes) to robustness checks.

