Appendix C. Randomization Procedures

Variables Randomized. Study participants are randomized with respect to:

- 1) Intervention video vs. no intervention video
- 2) Pure control vs. attention placebo control (among those randomized to no intervention video)
- 3) 20 Rand vs. 5 Rand cost to reserve spot at job search skills workshop
- 4) Male-vs.-female-oriented HIV transmission questions

1. Intervention video vs. no intervention video

Level of randomization. Individuals are randomized to video intervention vs. control. Randomization is at the bounded structure level, so that all respondents within a bounded structure get the same treatment.

Stratification. Randomization is stratified by weekblock to ensure approximately equal numbers of treated and controls within weekblocks.

Constrained (restricted) randomization. The AHRI data contain robust information on baseline covariates. However, because randomization is at the level of the bounded structure, it was not possible to stratify by individual characteristics. Instead, we use a constrained (aka restricted[25]) randomization approach. For the primary analysis – comparison of intervention video vs. no intervention video, we constrained randomization to force balance on the following characteristics: sex, age, whether the person was in school, orphan status, HIV positive status, HIV negative status (unknown is the third category), and household asset quintile. We randomized the intervention treatment assignment (intervention video vs. no intervention video) 3078 times using different randomization seeds. Each time, we assessed balance on key characteristics through a t-test (i.e regression of treatment assignment on the covariate). All randomization seeds that lead to a maximum t-test value greater than 1.68 ($p<0.1$) were excluded. This excluded 62% and retained 38% of the seeds (1060 seeds). We then randomly selected two seeds from these 1060 acceptable seeds. One was used to randomize the video, the other was used to randomized the incentive for the job search skills workshop. We assessed correlation of these two interventions and re-randomized if the Chi2 p-value for the cross-tab was less than 0.5 (see tables below).

2. Pure control vs. attention placebo control (among those randomized to no intervention video)

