Within the control group – i.e. individuals assigned to “no intervention video” – we used simple randomization to assign respondents to “pure control” (no video) and to “attention placebo control” (video on another topic).

3. 20 Rand vs. 5 Rand to reserve spot at job search skills workshop

Participants were given 30 or 15 Rand and were then asked to pay 20 or 5 Rand respectively to reserve a spot in the job search skills workshop. Randomization was conducted as described above in concert with the intervention video comparison.

4. Male-vs.-female-oriented HIV transmission questions.

In the survey, respondents were asked to report on the chances that an HIV-negative woman (man) would become HIV-infected after having sex with an HIV-positive man (woman). We used simple randomization to assign respondents to the male-focused or female-focused HIV transmission questions.

Data management procedures

These random treatment assignments – video assignment, job search workshop incentive assignment, together with their AHRI internal ID numbers were submitted to the AHRI data management core, which linked them with the operational data.

Blinding

The investigators are blinded to randomization assignment throughout data collection, cleaning, and development of the analysis plan. Randomization status with respect to the intervention and placebo videos will not be revealed until after all data on the primary outcome (including uptake of testing in the 2017 AHRI surveillance) have been collected, the data have been cleaned, and final pre-analysis plan is posted.[26]

Tables. Intervention video stratified by weekblock and approximately balanced vs. Job Skills Workshop incentive

tab week TreatmentArm				
week	TreatmentArm		Total	
	C	T		
34	60	60	120	
35	60	60	120	
36	60	60	120	
37	61	59	120	
38	60	60	120	
39	60	60	120	
40	59	61	120	
41	62	58	120	
Total	482	478	960	

tab TreatmentArm JobWorkshopArm, chi2				
TreatmentA rm	JobWorkshopArm		Total	
	C	T		
C	245	237	482	
T	243	235	478	
Total	488	472	960	

Pearson chi2(1) = 0.0000 Pr = 0.998

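### B4(c) picks extra covariates by a baseline p<0.1 test, so most change-score outcomes are adjusted for their own baseline only when chance imbalance triggers it

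*Combined protocol and SAP*

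**What the plan says.** B3 sets out the balance checks: "For each baseline covariate, we will report a t-test for the null hypothesis of equal means in Arm 1 vs. Arms 2+3 (pooled". The candidates are the variables used in the constrained randomisation, every primary or secondary outcome measured at baseline, and five variables linked from the surveillance.

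B4 then builds the adjusted estimates from three groups of covariates:

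- (a) week-block and the constrained-randomisation variables, always included;
- (b) three predictors named in advance, always included: distance to clinic, baseline subjective life expectancy, and baseline belief about lifetime HIV risk;
- (c) a conditional group: "Finally, to eliminate imbalances on observables, we will adjust for variables with" p<0.1 "for the t-test of differences between Arm 1 and Arm 2+3".

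The example results table has three estimate columns: crude, design-adjusted, and fully adjusted. Only the last uses (c). The same columns are filled for the pooled comparison and for comparisons A (Arm 1 vs 2) and B (Arm 1 vs 3). Footnote b describes the trigger differently: "variables that were not balanced at baseline despite randomization (p-value <0.1 in F-test".

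B4 defines change outcomes as within-subject differences. It says of the crude outcome regressions, "We will adjust our standard errors for clustering at the household level", and B6 repeats this for the logistic models. B3 does not mention clustering. Within the control group, Appendix C says "we used simple randomization to assign respondents to" pure control or attention placebo.

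**The concern.** B4 itself gives reduction of residual variance as the reason for including strong predictors. Group (c) selects on something else. Under randomisation, a baseline difference at p<0.1 is largely chance, so (c) admits variables whether or not they predict the outcome and passes over predictive ones that happen to be balanced.

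This matters most for change scores. A change score is normally correlated with its own baseline, so that baseline is the obvious covariate. Group (b) supplies it for subjective life expectancy and for lifetime HIV risk belief. It does not for 12 other secondary outcomes: time use, self-reported savings, the health-risk index, condomless sex, HIV care-seeking, community life expectancy, work and schooling beliefs, future orientation, the two locus-of-control indices, life satisfaction and mental health. For these, a baseline p-value decides whether the third column is a plain change-score comparison or a baseline-adjusted one.

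The trigger also looks only at the pooled contrast, yet its list is used for A and B. Arms 2 and 3 were separated outside the balance constraint, so the pooled test can miss imbalance in either separate comparison.

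**Working it through.** **The plan's own figure.** A7 gives 80% power for 0.26 SD with 450 participants, 1:1 pooled. With 225 per group and two-sided 0.05 (assumed from the 95% intervals), the detectable difference is (1.960 + 0.842) × √(2/225) = 0.264 SD, which rounds to 0.26. Power at exactly 0.26 is 78.7%. The figure reproduces. I use 0.265 SD below, where unadjusted power is close to 80%.

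**How many variables depend on (c).** Counting one variable per outcome heading, 14 outcomes are measured at baseline, of which two are already in (b), leaving 12. Of five linked variables, clinic distance is in (b), leaving 4. So 16 can enter only through (c).

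- Expected flags by chance: 16 × 0.1 = 1.6.
- P(at least one) = 1 − 0.9^16 = 81%.
- Splitting life satisfaction (today, in five years) and work/schooling beliefs (two) gives 18: 1.8 expected, 85%.

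The probabilities assume independent tests. Correlation among the attitude indices would change them.

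**Plausible correlation of a change score with its baseline.** With equal variances and pre–post correlation ρ, |r| = √((1 − ρ)/2): 0.50 at ρ = 0.5 and 0.32 at ρ = 0.8. The documents give no ρ, so r = 0.3 to 0.5 is an assumption.

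**Power for one such outcome (225 per group, 0.265 SD, independent individuals).** SE = √(2/225) = 0.0943, and 0.265/0.0943 = 2.811.

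- Never adjusted: Φ(2.811 − 1.960) = 80%.
- Always adjusted: Φ(2.811/√(1 − r²) − 1.960) = 84% at r = 0.3 and 90% at r = 0.5.
- Under the rule: the baseline is unflagged with probability 0.9. Its standardised imbalance is then confined to ±1.645, with variance 1 − 2 × 1.645 × φ(1.645)/0.9 = 0.623. The unadjusted statistic then has SD √(0.623r² + 1 − r²), which is 0.983 at r = 0.3 and 0.952 at r = 0.5. Power when unflagged is Φ(0.851/0.983) = 80.7% and Φ(0.851/0.952) = 81.4%.
- Overall under the rule: 0.9 × 80.7% + 0.1 × 83.8% = 81.0% at r = 0.3; 0.9 × 81.4% + 0.1 × 90.1% = 82.3% at r = 0.5.

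Type I error by the same route at r = 0.5 is 0.9 × 3.9% + 0.1 × 5% = 4.0%. Simulation agrees: power 81–82% under the rule, type I error 4.0–4.4%.

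**Cost against making no such adjustment.** For a flagged covariate with no predictive value, the SE factor is 1/√(1 − t²/(448 + t²)): 0.3% wider at t = 1.645 and 1.0% at t = 3. If it explains 5% of outcome variance, the SE is about 2% narrower. In a household-assigned simulation with 18 independent candidates, mean SE under the rule ran from about 1% wider to 2% narrower than without it.

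**Cost against a fixed list.** In that simulation (mean household size 1.3, assumed; groups (a) and (b) omitted):

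| Variance explained by each candidate | Mean SE, all 18 fixed | Mean SE, rule (c) | Rule ÷ fixed |
|---|---|---|---|
| 0% | 0.0983 | 0.0976 | 0.99 |
| 0.5% | 0.0936 | 0.0974 | 1.04 |
| 1% | 0.0890 | 0.0973 | 1.09 |
| 2% | 0.0786 | 0.0969 | 1.23 |

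**Pooled trigger.** With 50/25/25 allocation, the pooled contrast and the Arm 1 vs 2 contrast correlate 2/√(2 × 3) = √(2/3) = 0.816. From the bivariate normal, 4.8% of covariates pass p<0.1 in Arm 1 vs 2 but not in the pooled test. That is 48% of the 10% that are imbalanced there. The same holds for Arm 1 vs 3.

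**The case against.** The strongest defence is that the plan is more disciplined than it may look. Threshold, contrast and candidates were posted before unblinding; selection uses no outcome data; and the crude and design-adjusted columns stand beside the third. All of this stands. It rules out the inference that analysts may choose covariates freely or that the rule raises false positives. Simulated type I error was 3.5–5.7%, and where it reached 5.7% the model without the rule gave 6.0%.

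Second, (a) and (b) already fix the main covariates. Among the primary outcomes, the life-expectancy change has its baseline in (b) and the attitudes index has no baseline. This stands and confines the power loss mainly to secondary outcomes.

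Third, households were randomised before recruitment, and B3 says balance among those actually recruited is unknown. That is a good reason to report balance and to keep a sensitivity analysis. Recruitment is blinded, however, so imbalance remains mainly a matter of chance, and a p-value is still a poor guide to which variables predict the outcome.

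Three stronger readings are tempting and not supported:

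- *The balance tests ignore household assignment.* B3 is silent; it does not say they are unclustered. If they were, the 10% flag rate would become 15% at a design effect of 1.3 and 24% at 2.0 (assumed values). Only three of the 16 candidates (household size, household HIV death, household ART) are described at household level. No balance results appear in the documents, so none can be called wrong.
- *The rule loses precision.* It does so only relative to a fixed prognostic list.
- *The t-test and F-test select different variables.* For one covariate and two groups F = t², so the p-values are identical. They would differ only for a three-arm or joint F-test, which footnote b does not specify.

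**Conclusion.** The point holds as a minor one about efficiency and pre-specification. Group (c) leaves the covariates of one column to chance imbalance, and the list cannot be known until assignments are. Its cost is precision forgone on the 12 secondary change outcomes: about 81–82% power instead of 84–90% at 0.265 SD and n = 450, if baseline and change correlate 0.3 to 0.5. That correlation is assumed, and the calculation treats individuals as independent and sets aside any variance already explained by (a) and (b). For comparisons A and B, the rule also misses about half of the imbalances it is meant to catch. Nothing here indicates bias or inflated type I error, and the primary outcomes are little affected.

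**What to change.** - In B4, replace (c) with a list fixed in advance: (a), (b) and, for each change outcome, its own baseline value. Use the same list for the pooled comparison and for A and B.
- Keep imbalance-triggered adjustment only as a labelled sensitivity analysis.
- In B3, report standardised differences for Arm 1 vs 2+3, 1 vs 2 and 1 vs 3. If p-values are kept, state that they come from regressions with week-block indicators and standard errors clustered at the unit of assignment. Name that unit: A8.2 says "treatment assignment will be determined at the level of the household", while Appendix C says "Randomization is at the bounded structure level, so that all respondents within a bounded structure get the same treatment".
- Correct footnote b so that it describes the same model as B4.

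The cost is wording only, with no new data. The downside is that a chance imbalance in an unlisted variable is shown in the balance table but adjusted for only in the sensitivity analysis. One fixed list does not remove every imbalance in A or B either; its merit is that it is known beforehand and chosen for predictive value.

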Theory predicts that the impact of the video on subjective life expectancy (and human capital investment behaviors) should be greater the lower the person's baseline survival expectations, as the informational intervention is stronger relative to the person's baseline beliefs. Additionally, theory predicts that the impact of the video on subjective life expectancy (and human capital investment behaviors as well as HIV testing) should be greater the higher a person's baseline perceived lifetime risk of HIV acquisition, as information on the life-prolonging benefits of ART will be irrelevant to someone who believes that they are unlikely ever to contract HIV.

Therefore, we will test the null hypotheses that subjective life expectancy and perceived lifetime HIV risk are not linear effect modifiers of the primary outcomes: change in subjective life expectancy, HIV testing (with the voucher or home-based testing), participation in the training workshop, savings, and the pooled behavioral outcome described above.

The benefits of HIV testing vary with prior knowledge of status. Individuals who are certain that they are HIV-infected and individuals who are certain that they are HIV-uninfected have little incentive to test, suggesting an inverse-U relationship.

Therefore, we will assess for effect modification of the impact of the video on HIV testing by current beliefs about HIV infection, comparing effects among respondents with greater uncertainty about HIV status vs. those with greater stated certainty.

Finally, we will assess for linear effect modification by age (the information may be more impactful on younger participants who have yet to establish behavioral patterns) and sex (a common effect modifier in HIV interventions).

A5. Overview of Study Design

We will conduct a pilot intervention study to learn whether a short video providing young adults with information on recent longevity gains affects survival expectations, hope for the future, and ultimately health and educational behaviors. We intend to recruit approximately 450 young adults ages 18 to 25 for this research project. The study involves the following components:

- Conduct a survey to measure survival expectations and other perceptions of HIV and ART that affect health decision-making as well as health and education (future-oriented) actions,

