Definition: We will assess changes between baseline and 2-month follow-up in self-reported unprotected sex. Specifically, we will assess number of times a person reported having condomless sex in the last 30 days.

[Time Frame: 2 months]

Change in self-reported current HIV care-seeking

Definition: We will assess change between baseline and 2-month follow-up in a combined self-report measure of whether the respondent either tested for HIV within the last 3 months and whether the respondent is currently taking ARVs.

[Time Frame: 2 months]

Employment, education, and care-seeking outcomes in the AHRI surveillance

Definition: We will assess longer run education, employment, migration, and care-seeking outcomes observed through household proxy report and clinic linkage in the AHRI population-based surveillance platform. Specifically, we will assess whether the respondent is reported to be in school, working, looking for work, or none of the above; whether the respondent is still residing in the surveillance area; and whether the respondent has linked to clinical HIV services.

[Time Frame: 1 year, 2 years]

Attitudes and beliefs

Change in beliefs about life expectancy in the community

Definition: at baseline and at 2-month follow-up, we ask people to consider 20 people their age and gender in the community and to estimate how many they think will be alive at age 30, 40, ... 80. We will construct a measure of perceived community life expectancy by linearly interpolating the responses to these questions (starting at the respondent's age) and computing the area under the curve. This value is the average number of years they expect a demographically similar person in the community to live.

[Time Frame: 2 months]

Change in beliefs about lifetime risk of HIV infection

Definition: change between baseline and 2-month follow-up in the subjective probability (out of 20) of becoming HIV-infected at some point in their life. Although we do not expect that the video will change underlying beliefs about HIV risk; it could change people's willingness to consider these risks, which would be important to know in interpreting our results.

[Time Frame: 2 months]

Change in beliefs about work and schooling

Definition: At baseline and 2-month follow-up we asked respondents about the chances (out of 20) that they would complete different levels of schooling and about the chances they would be employed in the future. We will assess changes in these beliefs.

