Logistic regression model. We will also estimate our primary models using multivariate logistic regression to assess sensitivity to specification. In lieu of odds ratios, we will report marginal effects associated with the treatment arm, to enable comparison with the estimate from the OLS models. Again, standard errors will be clustered at the household level.

Restrict to HIV-uninfected. HIV testing uptake – one of our primary outcomes – is less relevant for individuals who already know their current HIV status. In a robustness check, we will assess HIV uptake after excluding: individuals who reported that they had ever tested for HIV and were certain that they were HIV positive at baseline (20 out of 20 beans); and individuals who reported testing for

HIV in the prior 3 months and reported that they were sure that they were HIV negative (0 out of 20 beans).

Remove participants with inconsistent answers and extreme outliers. A small number of participants reported inconsistent answers to the survival expectations questions at baseline. We will assess robustness of results after removing: participants who reported non-zero chances of survival at ages greater than the “oldest possible age” they could imagine living to; participants who reported that it was unlikely they would live to 60 years but allocated >10 beans; participants who reported that it was likely they would live to 60 years but allocated <10 beans. Demographic differences between persons with consistent and inconsistent answers will be reported.

B7. Adjusting Inference for Multiple Hypothesis Testing

No adjustments will be made for our primary outcomes.

For secondary outcomes, the primary manner in which we adjust for multiple hypotheses being tested is by grouping outcomes into indices such that their joint significance will be tested. If we do not find that there is overall significance for aggregated measures of behaviors such as local of control, we will not move test statistical significance of individual index components. In addition, for families of outcomes where we are interested in testing the treatment effect both for an index overall as well as individual components, when the number of tests is large (greater than 10), we adjust our standard errors using the Benjamini-Hochberg procedure[24] for controlling the false discovery rate to less than 0.05.

B7. Handling attrition

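### The lifetime-HIV-risk interaction for HIV testing is fitted in all participants, although the plan says people sure of their status have little reason to test; it needs a companion fit under both B6 exclusions

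*Combined protocol and SAP*

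**What the plan says.** The interaction is planned in two places. In A4 (Subgroup analyses) the sponsor writes: "we will test the null hypotheses that subjective life expectancy and perceived lifetime HIV risk are not linear effect modifiers of the primary outcomes". HIV testing and the pooled behavioural outcome are among the outcomes named there. B5 repeats the plan: "We will assess for linear effect modification of our primary outcomes by perceived lifetime infection risk". Neither section restricts the population.

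A4 predicts a larger effect at higher perceived risk, because "information on the life-prolonging benefits of ART will be irrelevant to someone who believes that they are unlikely ever to contract HIV". B1.2 defines the item as "the subjective probability (out of 20) of becoming HIV-infected at some point in their life".

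The next paragraph of A4 gives a different pattern for testing, by certainty about current status: "Individuals who are certain that they are HIV-infected and individuals who are certain that they are HIV-uninfected have little incentive to test". It calls this an inverse U and plans a separate analysis, "comparing effects among respondents with greater uncertainty about HIV status vs. those with greater stated certainty". B5 does not list that analysis.

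B6 (Restrict to HIV-uninfected) re-checks testing uptake after two exclusions. The first is "individuals who reported that they had ever tested for HIV and were certain that they were HIV positive at baseline", defined as 20 of 20 beans. The second is people who tested in the prior 3 months and were sure they were negative, at 0 of 20 beans. B6 opens by limiting its checks to the primary comparison, Arm 1 against Arms 2+3.

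**The concern.** HIV-positive young adults are in the sample. A6 does not exclude them, the randomization is balanced on HIV-positive status, and B1.2 defines a care outcome for infected participants. Someone who knows they are infected would plausibly answer at or near 20 on a lifetime-risk question. A4 expects the largest effect on testing at that end of the scale, but it also says people certain of infection have little reason to test.

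One linear term across everyone mixes these two groups at the point of highest leverage. HIV status enters the B4 models only as a main effect, which cannot absorb a different video effect in known positives. At stake is the test of a theoretical prediction. The trial could report weak or no modification of testing by perceived risk when the prediction holds in people for whom testing is relevant, or a negative slope when there is no modification among them.

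**Working it through.** **Stated figure.** The plan gives power only for the main effect: 0.26 SD with 450 participants (A7). With 225 per group, 80% power and two-sided alpha 0.05 (assumed; not stated), the detectable difference is (1.960 + 0.842) × √(2/225) = 0.264 SD, so the figure reproduces. No figure is given for any interaction.

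**Model.** All inputs below are assumptions, because the documents give neither the score distribution nor the share of participants who know they are positive. Among everyone else the score X (0 to 20) has mean m and variance v, and the effect on testing is proportional to X, scaled to a slope of 1. A share f of known positives sits at 20 with effect e, where 20 would be the full predicted effect. The fitted slope, as a fraction of the true slope, is

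S = 1 − f(20 − m)(20 − e) / [v + f(20 − m)²]

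Example: m = 5, v = 18, f = 0.05.
- e = 0: S = 1 − 0.05 × 15 × 20 / (18 + 0.05 × 225) = 1 − 15/29.25 = 0.49.
- e = 10: S = 1 − 7.5/29.25 = 0.74.
- e = 20: S = 1.

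For the composite, three components with equal slopes are assumed and only testing is affected, so the retained fraction is (S + 2)/3. In the example this is (0.49 + 2)/3 = 0.83.

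If there is no true modification (a constant effect in everyone else, zero in known positives), the spurious change across the whole 0–20 scale is −20f(20 − m) / [v + f(20 − m)²], as a multiple of that constant effect. In the example this is −15/29.25 = −0.51.

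Results at f = 5%, which is 0.05 × 450 ≈ 22 people:

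| Assumed score distribution | m | v | Testing, e = 0 | Testing, e = 10 | Composite, e = 0 for testing | True zero slope becomes |
|---|---|---|---|---|---|---|
| Uniform 0–20 | 10 | 36.67 | 0.76 | 0.88 | 0.92 | −0.24 |
| Beta-binomial (1,3) | 5 | 18 | 0.49 | 0.74 | 0.83 | −0.51 |
| Beta-binomial (2,2) | 10 | 24 | 0.66 | 0.83 | 0.89 | −0.34 |
| Normal(5, SD 5), clipped to 0–20 | 5.42 | 18.71 | 0.50 | 0.75 | 0.83 | −0.50 |
| Normal(8, SD 6), clipped to 0–20 | 8.20 | 29.21 | 0.67 | 0.84 | 0.89 | −0.33 |

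With e = 0, the testing slope keeps 0.73 to 0.90 at f = 2% and 0.26 to 0.57 at f = 10%. The composite keeps 0.91 to 0.97 and 0.75 to 0.86. The testing slope changes sign at f = v / [m(20 − m)], which is 24% to 37%.

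**The other end of the scale.** Suppose instead that a share g of certain negatives sits at 0 with no effect, and everyone else has a constant effect. The spurious rise across the scale is +20gm / (v + gm²). At g = 10% this is 0.43 to 0.59 of that constant effect over the same five distributions; for m = 5 it is 20 × 0.1 × 5 / (18 + 0.1 × 25) = 10/20.5 = 0.49. If the true effect already falls to zero at a score of 0, certain negatives cause no distortion. Removing only certain positives would therefore leave a possible tilt toward the predicted direction.

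**The case against.** The strongest objection is that the mechanism is inferred. A reader might take the plan to place known positives at the top of the lifetime-risk scale. It does not say so. The 20 of 20 beans in B6 refers to current status, a different item, and the questionnaire is not in the documents. If known positives are not asked the lifetime item, they drop out and there is no bias of this kind. This stands as a limit on the claim. Against it, B4 lists baseline lifetime-risk belief as a covariate in the adjusted models, which suggests that it is scored for all participants.

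Zero effect is a further assumption: A4 speaks of incentive to test, not of the video's effect. With half the predicted effect the loss is halved, and with the full effect it disappears.

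A reader might also call the test biased toward zero. That is too general. The pull is downward: it weakens a positive slope at modest shares, can reverse it at large ones, and moves a true zero slope away from zero.

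Nor has the certainty analysis been dropped. A4 and B5 are parts of one document, and A4 still commits to it. It uses a different modifier, though, so it does not repair the lifetime-risk slope.

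Finally, this is a subgroup analysis in a pilot that says it can detect only large effects, and no primary estimate changes. That limits the importance of the point, but the remedy is equally small.

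**Conclusion.** The point holds as a modest gap in the analysis plan. B5 applies one linear term for HIV testing to everyone, while A4 and B6 recognise that testing means something different to people sure of their status. Nothing carries that recognition into the interaction.

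At a 5% known-positive share the testing slope keeps about 49% to 76% of a true positive value with no effect in that group, or about 74% to 88% with half the predicted effect. A true zero slope becomes a fall of 0.24 to 0.51 of the constant effect across the scale. These figures rest on known positives scoring 20 and on assumed shares and score distributions. The adult HIV prevalence of one third in A3 does not give the share of 18–25-year-olds who know they are positive.

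The composite is much less affected (about 83% to 92% kept at 5%), because testing is one of three components. A reader might infer that known positives should also leave the composite main effect. The documents do not support that: B6's reason concerns testing, and no passage predicts a smaller effect on workshop attendance or savings in this group.

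**What to change.** - In B5, for HIV testing, also fit the lifetime-risk interaction after applying both B6 exclusions: ever tested with 20 of 20 beans, and tested in the prior 3 months with 0 of 20 beans. Report it beside the all-participant fit. Using both rules avoids tilting the test in either direction.
- State how known positives are asked and coded on the lifetime-risk item. Their answers can be tabulated from baseline data without treatment assignment.
- For the composite interaction, do the same only as a sensitivity check. Leave the composite main effect unrestricted.
- List the A4 certainty-of-status comparison in B5.

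The cost is a few sentences, using pre-intervention items that B6 already relies on, and somewhat fewer participants and less precision in the restricted model. Known positives who do not report 20 of 20 beans would remain in it, so the restriction reduces the problem but may not remove it.
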